10.4 ANALYSES SETS

10.4.1 Modified Intent-to-Treat (mITT) Analysis Set

The Modified Intent-to-Treat (mITT) analysis set is a subset of the ITT set. This set will consist of all enrolled subjects who were vaccinated at least once with Sci-B-Vac™ and had at least one post study IP administration follow-up visit. This analysis set will serve as the primary analysis set for efficacy and safety inference.

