2.4 Study Populations

Up to ninety two (92) healthy subjects will be enrolled in the study

Intent-to-Treat (ITT) Population includes all enrolled subjects who were vaccinated at least once with Sci-B-Vac™. The Safety population will be same as ITT population.

Modified Intent-to-Treat (mITT) population is a subset of the ITT set. This set will consist of all enrolled subjects who were vaccinated at least once with Sci-B-Vac™ and had at least one post vaccination follow-up visit, fully comply with the study protocol, had no violation of any of the inclusion/exclusion criteria and did not demonstrate an anamnestic response after the 1st administration of Sci-B-Vac. An anamnestic response revealed by Sci-B-Vac is defined as anti-HBs level above 6000mIU/ml (the highest titer recorded upon Sci-B-Vac 1st injection) in a subject with no detectable anti-HBs antibody at visits 1 and 2. Subjects who early terminated the study but reached the primary endpoint will be included as well. Subjects who did not complete the full-course of vaccination (i.e. 3 injections) and did not reach SPR will be excluded from the mITT set. This analysis set will serve as the primary analysis set for efficacy and safety inference.

Full Treatment (FT) set is a subset of the mITT analysis set and will consist of all subjects who were vaccinated 3 times with Sci-B-Vac™ and had at least one visit following the 3rd vaccination.

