14.3.4-3	Incidence of Chemistry Abnormal Clinically Significant Results
14.3.4-4	Out of Range Chemistry Results
14.3.4-5	Incidence of Urinary Abnormal Clinically Significant Result
14.3.4-6	Out of Range Urinary Result
14.3.4-7	Pregnancy test (Females)
14.3.5	Other Safety Assessment
14.3.5	Summary statistics of Hematology results by Visit
14.3.6	Summary statistics of Hematology Changes from Baseline by Visit
14.3.7	Summary statistics of Chemistry results by Visit
14.3.8	Summary statistics of Chemistry Changes from Baseline by Visit
14.3.9	Summary statistics of Urinalysis results by Visit
14.3.10	Summary statistics of Urinalysis Changes from Baseline by Visit
14.3.11	Summary of Vital Signs by Visit
14.3.12	Frequency of Vital Signs Grading by Visit
14.3.13	Summary of Vital Signs Changes from Baseline (pre-vaccination) by Visit
14.3.14	ECG Assessment
14.3.15	Local Reaction
14.3.16	Any Change in Subject's Health and in concomitant medications since last visit

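### SAP 2.4 names two different sets for safety, and the laboratory, vital-sign, ECG and local-reaction tables carry no label to settle which applies

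*SAP*

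**What the plan says.** SAP 2.4 first defines the broad set: "Intent-to-Treat (ITT) Population includes all enrolled subjects who were vaccinated at least once with Sci-B-Vac™". It adds: "The Safety population will be same as ITT population".

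The next paragraph defines the mITT as a subset of ITT whose members must have "had at least one post vaccination follow-up visit, fully comply with the study protocol, had no violation of any of the inclusion/exclusion criteria". They must also show no anamnestic response after the first injection. Two further sentences deal with early leavers. One keeps some of them: "Subjects who early terminated the study but reached the primary endpoint will be included as well". The other removes some: "Subjects who did not complete the full-course of vaccination (i.e. 3 injections) and did not reach SPR will be excluded from the mITT set". The paragraph then closes: "This analysis set will serve as the primary analysis set for efficacy and safety inference".

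Protocol version 2.0, section 10.4.1, ends with the same closing statement but attaches it to a wider mITT, which asks only for one dose and one later visit: "This set will consist of all enrolled subjects who were vaccinated at least once with Sci-B-Vac™ and had at least one post study IP administration" (the sentence ends by naming that visit). Protocol section 10.4 defines no separate safety set.

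SAP 4.7 (safety analysis) does not name a population. In SAP Appendix I, the treatment-emergent AE summary and the AE and serious AE tables (14.3.1 to 14.3.1-4) are labelled ITT. Tables 14.3.4-1 to 14.3.16 are not labelled; an example is "Summary of Vital Signs by Visit".

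**The concern.** Two statements in one section assign safety to different sets, and both cannot hold. The mITT is an efficacy set. One of its rules makes membership depend on the immune response. Take two subjects who stop after the first injection because of the same adverse event. The one whose anti-HBs had reached 10 mIU/ml is kept, and the other is removed. Antibody response is no reason to count or ignore a safety observation.

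The subjects affected are ones the protocol wants to keep in view. Protocol 5.6 lists an adverse event as a reason for discontinuation, and 5.7 stresses follow-up of anyone withdrawn for an adverse event or an abnormal laboratory finding. The primary safety endpoint in the protocol synopsis includes clinically significant laboratory abnormalities, and the tables that count them (14.3.4-1, 14.3.4-3 and 14.3.4-5) are among those without a label. Two programmers could defensibly produce them on different sets, and one report could then carry AE and laboratory tables with unexplained differences in denominator.

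**Working it through.** The plan states no figure on this point, so the check is mainly textual.

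**Step 1. Who is in ITT/Safety but not in the SAP's mITT**

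| Vaccinated subject | ITT / Safety | SAP mITT | Protocol v2.0 mITT |
|---|---|---|---|
| No post-vaccination follow-up visit | in | out | out |
| Not fully compliant with the protocol, has a follow-up visit | in | out | in |
| Eligibility violation, has a follow-up visit | in | out | in |
| Anamnestic response, has a follow-up visit | in | out | in |
| Fewer than 3 injections, SPR not reached, has a follow-up visit | in | out | in |
| Early terminator who reached the endpoint, has a follow-up visit | in | in | in |

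The SAP carried the protocol's closing sentence onto a much narrower set.

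**Step 2. Which safety outputs have a stated set**

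| Output (SAP Appendix I) | Stated set |
|---|---|
| AE and serious AE summaries, 14.3.1 to 14.3.1-4 | ITT |
| Clinically significant and out-of-range laboratory results, pregnancy test, 14.3.4-1 to 14.3.4-7 | none |
| Laboratory summaries and changes, 14.3.5 to 14.3.10 | none |
| Vital signs, 14.3.11 to 14.3.13 | none |
| ECG, local reaction, change in health, 14.3.14 to 14.3.16 | none |

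The first row loses nobody. The other rows are ambiguous: the Safety = ITT sentence and the mITT sentence both claim them, and SAP 4.7 does not decide between them.

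**Step 3. Illustration of possible size**

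Inputs from the documents: up to 92 enrolled (SAP 2.4) and 70 in the sample size justification (SAP 2.6). Assumptions, because the documents give no values: the number k outside the mITT, and the event rates in retained and excluded subjects. I take k from 5 (arbitrary) to 92 − 70 = 22, which is 5/92 = 5% to 22/92 = 24% of those vaccinated. Even 22 is not a ceiling, because the full-compliance rule could remove more.

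Rate in all vaccinated = [(92 − k) × rate in retained + k × rate in excluded] / 92, with 10% in retained subjects:

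| Assumed rate in excluded | k = 5 | k = 22 |
|---|---|---|
| 0% | 8.7/92 = 9.5% | 7.0/92 = 7.6% |
| 10% | 10.0% | 10.0% |
| 30% | (8.7 + 1.5)/92 = 11.1% | (7.0 + 6.6)/92 = 14.8% |
| 50% | (8.7 + 2.5)/92 = 12.2% | (7.0 + 11.0)/92 = 19.6% |

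A table run on the mITT would show 10% in every cell. The direction depends on an event rate that the documents do not supply.

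If no event at all is seen in a table, the one-sided 95% upper bound is 1 − 0.05^(1/n): 3.2% at n = 92 and 4.2% at n = 70. This loss of precision is small. It could arise only in the unlabelled tables.

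**The case against.** The strongest reply is that the main safety results already rest on all vaccinated subjects. Every AE and serious AE summary table is labelled ITT. Protocol 6.4.3 and 6.4.6 require clinically significant vital-sign changes and laboratory results to be recorded as AEs, so these reach the ITT tables by that route too. SAP 3.2 lists all measured variables individually, and SAP 4.7.1 lists serious AEs for dosed subjects without reference to the mITT. Safety is descriptive in a single arm, so no test depends on the set. All of this stands. A reader might infer from the mITT sentence that subjects who withdraw for an adverse event vanish from the AE results; the table labels do not support that.

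A second reply is that a defined Safety population has no use except in safety analyses, so unlabelled tables are naturally read as ITT. Elsewhere the SAP did move from mITT to ITT: disposition and demographics use mITT in protocol 10.5 and 10.6 but ITT in SAP 4.1 and 4.2. The mITT sentence may therefore be a leftover. This also stands, as far as it goes. It would be equally wrong to say that the mITT sentence governs the unlabelled tables. The text supports ambiguity and nothing stronger.

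Third, by-visit laboratory and vital-sign summaries lack later values from withdrawn subjects whichever set is used. This is largely true. The choice still matters for the early visits, for reactions after injections 1 and 2, for the termination assessments that protocol 5.7 asks of those who withdraw, and for deviators who remain under follow-up.

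SAP Appendix II (listings) was not in the text available, so nothing is claimed about its labels.

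**Conclusion.** The contradiction in SAP 2.4 is real and should be corrected. As written, one rule would remove some vaccinated subjects from safety inference, partly according to antibody response, and SAP 4.7 does nothing to settle it. The practical exposure is confined to tables 14.3.4-1 to 14.3.16; for the AE and serious AE tables run as labelled, the loss is zero.

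The size of any bias is unknown. It is tempting to read the anticipated 20% withdrawal as the number lost (0.20 × 92 = 18.4 subjects), but the documents do not support that in either direction. Seroprotected early terminators stay in, withdrawal after the third injection does not trigger the incomplete-course exclusion, and deviators, eligibility violators and anamnestic responders are not part of the withdrawal figure.

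It is also tempting to say that safety rates on the mITT would be too low. That is plausible, since poor tolerability can cause early stopping, but the documents report no AE-driven withdrawal rates and it remains an expectation. The 11.1% to 14.8% range rests wholly on the assumed 10% and 30% event rates and on the assumed 5 to 22 exclusions.

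**What to change.** In the SAP:

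1. In 2.4, delete the words *and safety* from the sentence that names the mITT as the primary set.
2. In 4.7, state that all safety tables and listings (AEs, laboratory, vital signs, ECG, local reactions) use the Safety population, which equals ITT.
3. In Appendix I, add the ITT label to tables 14.3.4-1 to 14.3.16.

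This follows the SAP's own definition of the Safety population. It costs a few words and some table titles, with no new data or outputs.

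Protocol 10.4.1 should be aligned at the next amendment, which goes through the ethics route in protocol 11.8. The SAP change need not wait for it. Check the protocol version in force first: the SAP enrols up to 92 against 84 in protocol version 2.0, and its version history refers to protocol changes, so section 10.4.1 may already have been revised.

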2.5 Study Endpoints

Primary Endpoint:

Seroprotection rate (SPR), defined as the proportion of subjects with anti-HBs antibody titer at least equal to 10mIU/ml, at Month 7 (i.e. one month after the third immunization with Sci-B-Vac™). Subjects early terminated from the study for any reason at any time while having an anti-HBs antibody concentrations ≥ 10 mIU/ml will be considered among those who met endpoint.

Secondary Endpoints:

1. SPR one month after the first injection and at every month until Month 6 inclusive and at months 9 and 12.
2. Percentage of subjects with anti-HBs antibodies titer ≥ 100 mIU/ml at one month after the first injection and then at every month until Month 7 inclusive and at months 9 and 12.
3. The geometric mean concentration (GMC) as determined by anti-HBsAg antibody titers at Month 0, then at every month until Month 7 inclusive and at months 9 and 12.

Exploratory Endpoints:

1. The anti-preS1 antibody titers measured at Month 0, then at every month until Month 7 inclusive and at months 9 and 12.
2. The anti-preS2 antibody titers measured at Month 0, then at every month until Month 7 inclusive and at months 9 and 12.

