- Personnel and residents of public health institutions
- Persons at increased risk of the disease due to their sexual practices
 - Travelers to areas with high endemicity of HBV
 - Persons originating from areas of high endemicity
 - Users of illicit injectable drugs
- Military personnel, police personnel and anybody who through their work or personal lifestyle may be exposed to HBV
- Family members and others in intimate contact with persistent HBsAg-positive individuals.

Persons who develop anti-HBs antibodies following active infection with the hepatitis B vaccine are protected against the disease if they are re-exposed to the virus.

Clinical trials have shown that Sci-B-Vac induced protective levels of antibody in up to 100% of healthy adults who received the recommended three-dose regimen of 10 µg/dose.

Sci-B-Vac is highly immunogenic in children. The specific antibody titers tend to be an order of magnitude higher in children than in adults when the recommended doses are administered. Children tend to achieve seroprotection more frequently than adults.

Contraindications

Sci-B-Vac should not be administered to subjects with known hypersensitivity to any components of the vaccine or to subjects who developed symptoms suggestive of hypersensitivity after the injection of Sci-B-Vac.

As with other vaccines, the administration of Sci-B-Vac should be postponed in subjects suffering from acute severe illness. The presence of a minor infection, however, is not a contraindication for immunization.

Warnings

Due to the long incubation period for hepatitis B, it is possible for unrecognized infection to be present at the time of vaccination. Vaccination may not prevent hepatitis B in such individuals. The vaccine will not prevent infection caused by other agents such as hepatitis A, hepatitis C and hepatitis E or other pathogens known to infect the liver.

Precautions

General: As with any vaccine, epinephrine should be available for immediate use should an anaphylactic reaction occur.

Protocol No.: SciB018

Version and Date: Version 1.0, March 4, 2015

Caution and appropriate care should be exercised in administering the vaccine to individuals with severe compromised cardiopulmonary status or to others in whom a febrile or systemic reaction could pose a significant risk.

Sci-B-Vac should under no circumstances be administered intravenously.

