5.6 REMOVAL, REPLACEMENT, OR EARLY WITHDRAWAL OF SUBJECTS FROM TREATMENT OR ASSESSMENT

Subjects are free to discontinue their participation in the study at any time and without prejudice to further treatment. The Investigator must withdraw any subject from the study if that subject requests to be withdrawn, or if the subject present positive serological marker of hepatitis B infection, or it is determined that continuing in the study would result in a significant safety risk to the subject.

Subjects discontinued or withdrawn from the study will **not** be replaced after first dosing. If insufficient number of subjects are expected to complete the study, recruitment of additional volunteers will be considered. Approval by the IRB will be required.

The subject's participation in this study may be discontinued due to the following reasons:

- Positive serological marker for hepatitis B infection
- Request of regulatory agency, or Sponsor or Principal Investigator
- Subject withdrew consent
- Adverse event (AE)
- Subject is unwilling or unable to continue the study or is lost-to-follow-up

	Protocol No.: SciB018
	Version and Date: Version 2.0, September 9, 2015 Amendment 1

- Subject is non-compliant with study procedures/study protocol
- Investigator decides that withdrawal from the study is in the best interest of the subject
- Subject needs medication not allowed in the protocol
- Any clinically significant change in subject's medical condition.

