10.7.1 Primary Endpoint Definition and Analysis

The primary endpoint of the study is the Seroprotection rate (SPR), defined as the proportion of subjects with anti-HBs antibody titer at least equal to 10mIU/ml, at Month 7 (i.e. one month after the third immunization with Sci-B-Vac™). Subjects early terminated from the study for any reason at any time while having an anti-HBs antibody concentrations \geq 10mIU/ml will be considered among those who met endpoint.

	Protocol No.: SciB018
	Version and Date: Version 2.0, September 9, 2015 Amendment 1

The principal analysis of the primary endpoint will employ a non-inferiority analysis [SAS PROC FREQ with binomial (noninf margin=0.09 p=(1- α) exact)] statement will be used for testing the below hypothesis:

$$H_0: P-p_0 \leq -\text{Margin}$$

$$H_1: P-p_0 > -\text{Margin}$$

Where p_0 , the assumed true SPR is 95% and the non-inferiority margin is 9.0%, employing that study will be considered successful if the lower bound of the (1- α) exact CI will be 86.0% or more.

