2.3 Study Flow-chart

Visit Number	1	2	3	4	5	6	7	8	9	10	11
Visit Name	Screening	Treatment 1	Treatment 2	Follow-up	Follow-up	Follow-up	Follow-up	Treatment 3	Follow-up	Follow-up	Study Termination
Month (Week) of the Study	-1 ((-4) - 0)	0 (0 ¹)	1(4 ¹)	2(8 ¹)	3(12 ¹)	4(16 ¹)	5(20 ¹)	6(24 ¹)	7(28 ¹)	9(36 ²)	12(48 ²)
Activity											
ICF	X										
Demographics	X										
Inclusion/Exclusion	X	X									
Medical history	X										
Vital signs ³	X	X ⁴	X ⁴					X ⁴			X
Smoking status	X										
Weight, height, BMI	X										
Physical examination	X										X
Blood safety tests ⁵	X	X ⁶	X ⁶					X ⁶			X
Screening serology ⁷	X ⁸										
General urinalysis	X	X ⁶	X ⁶					X ⁶			X
Serum β-HCG	X										
Urine pregnancy test		X ⁶	X ⁶					X ⁶			X
12-lead ECG	X										X
Sci-B-Vac™ injection ⁹		X	X					X			
Local reaction grading		X ¹⁴	X ^{14,15}	X ¹⁵				X ¹⁴	X ¹⁵		
Serologic markers for hepatitis B infection	X ^{8,10}	X ^{6,11}	X ^{6,11}	X ¹¹	X ¹¹	X ¹¹	X ¹¹	X ^{6,11}	X ¹¹	X ¹¹	X ¹²
Serologic response to immunization ¹³		X ⁶	X ⁶	X	X	X	X	X ⁶	X	X	X
Sample for further investigations		X ⁶	X ⁶	X	X	X	X	X ⁶	X	X	X
Adverse Events	Recorded throughout the study										
Concomitant Medications	Recorded throughout the study										

- 1 \pm 3 days (Visit2/Treatment 1 may be performed up to 4 weeks +3 days from screening visit)
- 2 \pm 8 days
- 3 Sitting BP, HR, RR, oral temperature
- 4 Within 60 min before vaccine administration and at 60 (\pm 15) min after vaccination
- 5 CBC, blood chemistry, PT/INR (screening only) - see Appendix B
- 6 Prior to vaccine administration
- 7 Anti HIV (Ab type 1&2), anti-HCV Ab, anti-HAV IgM antibodies, ANA (See Appendix B)
- 8 Positive serology excludes from participation in the study
- 9 One IM injections of 1.0 ml into the deltoid muscle. The previous injection site will be inspected before the second and third administration. Subjects will remain for observation in the CRC for at least 1 hour after injections.
- 10 HBsAg, anti-HBs antibodies (also markers for previous vaccination), total anti-HBc antibodies and IgM anti-HBc antibodies.
- 11 HBsAg only.
- 12 HBsAg, Total anti-HBc antibodies and IgM anti-HBc antibodies
- 13 Anti-HBsAg, anti-preS1 and anti-preS2 antibodies
- 14 Local reaction grading after vaccination
- 15 Local reaction grading of previous vaccine administration and follow up until symptoms resolve

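### A subject withdrawn for a positive hepatitis B infection marker counts as seroprotected if anti-HBs is at least 10 mIU/ml, though that titre cannot be attributed to the batch

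*SAP*

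**What the plan says.** Four provisions act together.

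- **Withdrawal.** Protocol version 2.0, section 5.6, says the investigator must withdraw a subject "if the subject present positive serological marker of hepatitis B infection". The same section lists "Positive serological marker for hepatitis B infection" among the reasons for discontinuation. Section 5.6 of version 1.0 did not name infection.
- **Endpoint.** SAP 2.5 (repeated in 2.6 and 4.4) and protocol 3.1, 10.3 and 10.7.1 treat early leavers alike: "Subjects early terminated from the study for any reason at any time while having an anti-HBs antibody concentrations" at or above 10 mIU/ml "will be considered among those who met endpoint". There is no exception for infection.
- **Analysis set.** SAP 2.4 says of mITT, the primary set: "Subjects who early terminated the study but reached the primary endpoint will be included as well". SAP 2.8 and 4.4 repeat this. SAP 2.4 also removes from mITT anyone who had fewer than three injections and did not reach seroprotection.
- **Testing.** The SAP 2.3 flow chart schedules HBsAg alone as the infection marker at Visits 2 to 10, and at Visit 11 "HBsAg, Total anti-HBc antibodies and IgM anti-HBc antibodies". Table 14.2-15 in SAP Appendix I tabulates the infection markers for the ITT set, but no rule carries them into the seroprotection rate.

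The leaflet in protocol Appendix D warns that "it is possible for unrecognized infection to be present at the time of vaccination".

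**The concern.** The study asks what this batch elicits in people never infected with and never vaccinated against hepatitis B. A subject who becomes positive for an infection marker no longer answers that question, because the anti-HBs may come from the vaccine, from the infection, or from both. The plan nevertheless counts the titre as a vaccine success.

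The handling is also one-sided. Among infected subjects withdrawn before the third dose, one with anti-HBs of 10 mIU/ml or more is a success, and one below 10 leaves the denominator. Neither can count against the batch.

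The SAP already accepts the principle for a parallel case. SAP 2.4 excludes subjects with an anamnestic response, whose antibody does not show what the batch does in naive people. Infection on study has no matching rule.

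**Working it through.** **1. Does any existing rule remove such a subject?** Three candidates in SAP 2.4 and 4.4:

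- *Full compliance with the protocol.* Becoming infected is not clearly non-compliance.
- *No inclusion or exclusion violation.* Exclusion criterion 7 (positive HBsAg, anti-HBs, anti-HBc) has no on-study clause, whereas criterion 15 expressly extends through the trial. The flow-chart note that positive serology excludes from participation is attached to screening only.
- *Anamnestic response.* This needs anti-HBs above 6000 mIU/ml after the first injection and is aimed at earlier priming.

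None clearly applies.

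**2. Which subject is affected by the early-termination clause?** One withdrawn before a Month 7 titre. HBsAg is the only scheduled infection marker at Visits 2 to 10, so this is mainly a subject found HBsAg-positive with anti-HBs of at least 10 mIU/ml at termination. A subject who is HBsAg-positive at Month 7 with a qualifying titre counts as a success without needing the clause.

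**3. Inputs for the size.** SAP 2.6 gives an expected rate of 95%, a margin of 9.0%, hence a limit of 95% − 9% = 86%, and 70 evaluable subjects. The interval is exact binomial. The sample-size justification calls it one-sided 95%, while SAP 3.1 sets 5% two-tailed tests, so both bounds are shown.

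**4. Formula.** For x successes in n subjects, the Clopper-Pearson lower bound is the a-quantile of a Beta(x, n − x + 1) distribution, with a = 0.025 (two-sided 95%) or a = 0.05 (one-sided 95%).

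**5. The plan's own figure.** SAP 2.6 states a lower bound of 86.0% or more at n = 70 and a proportion of 0.95. Since 0.95 × 70 = 66.5, take 66 and 67. The bounds are 86.01% and 87.98% two-sided, 87.40% and 89.29% one-sided. The stated figure is reproduced.

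**6. Effect of one infected subject among 66 counted successes.**

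| Handling | Count | Two-sided bound | One-sided bound |
|---|---|---|---|
| Success (current rule) | 66/70 | 86.01%, pass | 87.40%, pass |
| Excluded | 65/69 | 85.82%, fail | 87.22%, pass |
| Not met | 65/70 | 84.11%, fail | 85.57%, fail |

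With 67 counted successes, one such subject does not change the result. Two counted as not met do (65/70); two excluded do not (65/68: 87.64% and 88.99%).

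**7. How often would the count sit exactly at the threshold?** At n = 70 the minimum passing count is 66 on either bound. The binomial probability of exactly 66 is 0.183, 0.194 or 0.131 for an assumed true rate of 93%, 95% or 96.5%. These are probabilities of being at the threshold. They say nothing about how likely an infection is.

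**The case against.** The strongest reply is that the case is very narrow. Subjects enter negative for HBsAg, anti-HBs and anti-HBc, and HBsAg is drawn again before dosing at Visit 2, when eligibility is reviewed. The affected subject must then be positive for an infection marker and also have anti-HBs of at least 10 mIU/ml. The documents give no infection rate, and with no cases there is no effect. This stands, and it limits the weight of the point. The descriptive FT analysis also drops anyone withdrawn before the third dose, but it is not the primary analysis.

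Three stronger readings are tempting and are not supported.

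- A reader might take the 13% to 19% in step 7 as the risk of a wrong verdict. They apply only if a misclassified subject exists and is recoded as a failure. The unconditional risk is smaller and cannot be computed from the documents. It also depends on handling and sample size: at 84 subjects, 79/84 has a two-sided bound of 86.65%, and excluding one subject leaves 78/83 and 86.50%, still a pass.
- A reader might infer that the flow chart itself classes anti-HBs as a marker of infection, because a footnote lists "HBsAg, anti-HBs antibodies (also markers for previous vaccination), total anti-HBc antibodies and IgM anti-HBc antibodies". That footnote belongs to screening only. After vaccination anti-HBs sits in a separate row for response to immunization.
- A reader might conclude that such a titre must come from the infection. It may be wholly vaccine-induced. The supportable statement is that its source cannot be told apart.

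**Conclusion.** The concern holds in a limited form. A stated rule, not merely a missing detail, lets antibody that cannot be attributed to the batch count toward the rate that qualifies it. When that misleads, it does so in the batch's favour.

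The documents do not support saying that this will bias the result. The number of such subjects is unknown; zero is plausible, and 0 to 2 is an assumption. At 70 evaluable subjects, one case changes the outcome at 66 counted successes if it is counted as a failure (either bound), or if it is excluded and the two-sided bound is used. At 67, two cases counted as failures would be needed.

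The gap is worth closing because the repair needs no new data, and because deciding after the titres are known would leave a favourable choice open.

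**What to change.** - **Endpoint wording** (SAP 2.5, 2.6 and 4.4; protocol 3.1, 10.3 and 10.7.1): after *for any reason*, insert *other than a positive serological marker of hepatitis B infection*.
- **Analysis set** (SAP 2.4): exclude from mITT any subject with a positive infection marker (HBsAg, or anti-HBc where tested) from Visit 2 up to and including the Month 7 visit or earlier termination. This matches the handling of anamnestic responses. SAP 2.7, 2.8 and 4.4, which add early leavers back, should refer to this exclusion.
- **Sensitivity analyses:** one counting these subjects as not having met the endpoint; and, at the final analysis, one that also excludes subjects first found anti-HBc positive at Visit 11.

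The window ends at Month 7 so that a subject with a valid Month 7 titre who first turns positive later is not removed retroactively from the primary analysis. Anti-HBc after screening is scheduled only at Month 12, so the interim analyses in SAP 2.7 must rely mainly on HBsAg.

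The cost is a few sentences. HBsAg is already tested at every visit and anti-HBc at Visit 11, and early leavers should undergo the termination assessments, which include serology (protocol 5.7 and 6.1.11). The downside is a rate that may be lower, or a denominator smaller, by one or two subjects. The withdrawal rule itself is unchanged.

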5.7 HANDLING OF WITHDRAWALS

If a subject is withdrawn from the study or fails to return either at his/her request or at the Investigator's discretion, every effort should be made to determine the reason. This information will be recorded on the subject's case report form (CRF). All subjects who withdraw from the study prematurely, regardless of cause, should undergo all study termination assessments (see Section 6.1.11). It is crucial to obtain follow-up data for any subject withdrawn because of an AE or abnormal laboratory test finding. In any case, every effort must be made to undertake safety follow-up procedures.

If withdrawal is caused by a Suspected Unexpected Serious Adverse Reaction (SUSAR), it will be reported to the institutional review board/independent ethics committee (IRB/IEC) and Sponsor.

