5.9 TERMINATION OF STUDY

A subject will be considered to have completed the study if he or she has completed all assessments at Month 12 of the study.

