8 STUDY RESTRICTIONS

8.1 CONCOMITANT MEDICATIONS

The following medications are prohibited for use by the subject throughout the study:

- Systemic corticosteroid treatment less than 14 days before first vaccination and throughout the study.
- Immunosuppressant medications (e.g. mycophenolate mofetil, cyclosporine, cyclophosphamide etc.)
- Biological immune-modifying agents (e.g. anti TNF alfa, anti CD20)

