3. STATISTICAL METHODS

3.1 General

The overall significance level for this study will be 5% using two-tailed tests.

The data will be analysed using the SAS ® version 9.3 or higher (SAS Institute, Cary North Carolina).

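### The early-termination success rule is not limited to exits before the Month 7 sample, so a measured Month 7 failure who leaves later with a titre of 10 mIU/ml or more could be counted as a success

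*SAP*

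**What the plan says.** SAP 2.5 sets the primary endpoint as the proportion of subjects with anti-HBs of at least 10 mIU/ml "at Month 7 (i.e. one month after the third immunization with Sci-B-Vac™". The next sentence extends success: "Subjects early terminated from the study for any reason at any time while having an anti-HBs antibody concentrations" of 10 mIU/ml or more are placed among those who met the endpoint. The same rule stands in SAP 2.6 and 4.4 and in protocol version 2.0, sections 3.1, 10.3 and 10.7.1.

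Four other provisions decide how far the rule reaches:

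- **Completion.** Protocol 5.9: "A subject will be considered to have completed the study if he or she has completed all assessments at Month 12 of the study". Leaving between Month 7 and Month 12 is therefore early termination.
- **Exit titre.** Protocol 5.7: "All subjects who withdraw from the study prematurely, regardless of cause, should undergo all study termination assessments". Protocol 6.1.11 includes serology among those assessments, and a Month 9 sample is also scheduled.
- **Analysis set.** SAP 2.4 requires mITT subjects to "fully comply with the study protocol, had no violation of any of the inclusion/exclusion criteria", then adds: "Subjects who early terminated the study but reached the primary endpoint will be included as well". SAP 2.8 describes the final analysis as compliant subjects who completed 12 months plus early terminators who achieved the endpoint before withdrawal.
- **Other vaccine.** Protocol 8.1 introduces its list with "The following medications are prohibited for use by the subject throughout the study". The list names corticosteroids, immunosuppressants and biological immune-modifying agents, but not non-study hepatitis B vaccine.

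**The concern.** The trial qualifies a batch by the response one month after the third study dose. The early-termination rule has no time limit and no order of precedence. Read literally, it lets a later exit titre replace a Month 7 titre that was actually measured. The later value could reach 10 mIU/ml through a late rise, through assay variation near the cut-off, or through a vaccine dose given outside the study.

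Where the rule changes a measured Month 7 result, it can only turn a failure into a success. With few failures expected, a single reclassified subject can decide the result.

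**Working it through.** **Inputs.** n=70 evaluable, expected rate 95%, margin 9 points, success if the exact lower bound is at least 86.0% (SAP 2.6 and 4.4). On sidedness, SAP 3.1 says "The overall significance level for this study will be 5% using two-tailed tests", while the sample-size justification in SAP 2.6 uses a one-sided 95% interval. Both are shown.

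**Formula.** Clopper-Pearson lower bound = Beta quantile(a; x, n−x+1), with a=0.025 (two-sided 95%) or a=0.05 (one-sided 95%).

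**The plan's own figure.** 0.95×70 = 66.5. At 66/70 the bound is 87.4% one-sided and 86.01% two-sided. The statement that n=70 gives 86.0% or more is reproduced.

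**Decision threshold at n=70.**

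| Successes | Two-sided bound | One-sided bound | Result |
|---|---|---|---|
| 65/70 | 84.1% | 85.6% | fail |
| 66/70 | 86.01% | 87.4% | pass |

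The threshold is 66 under either reading, so four failures are allowed. Expected failures at 95% are 70×0.05 = 3.5. The probability of landing exactly one success short, P(X=65 | 70, 0.95), is 13.5%.

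**Worst case: exactly one failure converted in every trial.** Passing then needs 65 true Month 7 successes.

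- True rate 86%: P(X≥66) = 2.5% becomes P(X≥65) = 6.1%.
- True rate 90%: 15.9% becomes 28.7%.

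**Proportional case (assumed range).** Suppose each Month 7 failure converts with probability f. The apparent rate is p+(1−p)f.

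| f | Apparent rate at p=86% | P(pass) |
|---|---|---|
| 0 | 86.0% | 2.5% |
| 1% | 0.86+0.14×0.01 = 86.14% | 2.7% |
| 5% | 0.86+0.14×0.05 = 86.7% | 3.5% |

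The documents give no value for f.

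**Larger n.** The chance of falling one success short at a true 95%, with the two-sided interval, is 11.6% at n=84 (the protocol's enrolment) and 8.7% at n=92 (the enrolment in SAP 2.4).

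**If the subject is excluded instead.** 65/70 becomes 65/69. The bound is 85.8% two-sided (fail) and 87.2% one-sided (pass). Exclusion therefore also moves the result towards success and, on the one-sided reading, changes the decision.

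**Which text keeps the failure?** SAP 2.4 drops non-responders only if they did not receive all three injections, so a three-dose failure who leaves after Month 7 could stay in. SAP 2.8 limits the final analysis to 12-month completers and early terminators who achieved the endpoint, which would leave that subject out. Nothing settles the conflict.

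**The case against.** The best counter-argument is that the rule was meant only to stand in for a missing Month 7 value. Protocol 10 and 10.1 time the interim analysis by subjects who have either reached Month 7 or terminated early, which treats these as alternatives. SAP 2.7, 2.8 and 4.4 speak of early terminators who reached or achieved the primary endpoint before leaving, and someone measured below 10 at Month 7 did not naturally reach a Month 7 endpoint. This is a plausible account of the intent, but none of these passages says so, and the endpoint sentence itself has no such limit.

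A reader might go further and infer that a Month 7 non-responder who is revaccinated outside the study and then leaves will be counted as a success. The documents do not support that. They never mention off-study revaccination, the rule requires a titre of at least 10 mIU/ml at exit, and the compliance condition in SAP 2.4 might remove such a subject. It is also not a defect that a subject at or above 10 at Month 7 who later falls stays a success, or that a completer below 10 at Month 7 who later rises stays a failure. Both are correct for a Month 7 endpoint.

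Some protection exists. Receipt of blood or immunoglobulin during the trial is already exclusion criterion 15, concomitant medications are recorded throughout, and SPR is tabulated by month, so a discrepancy at Month 7 would probably be visible. These points lower the likely frequency. They do not say which value decides the primary endpoint.

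**Conclusion.** The point stands as a gap in the endpoint definition. As written, the rule could override an observed Month 7 failure when the subject leaves before Month 12 with a titre of 10 mIU/ml or more, and no text clearly keeps that failure in the analysis. It cannot be said that such a subject will be counted as a success, because the SAP leaves the conflict between its compliance condition and its early-terminator sentence unresolved.

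The effect is probably small. It is 2.5% to 6.1% at a true rate of 86% only if one conversion occurs in every trial, and 2.5% to between 2.7% and 3.5% if 1% to 5% of Month 7 failures convert. These figures assume n=70 and the exact-interval criterion of SAP 4.4; the conversion rates are assumptions. The gap still merits closing, because one subject can decide the result.

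**What to change.** Add the following to SAP 2.4, 2.5, 2.6, 2.8 and 4.4 and to protocol 3.1, 10.3 and 10.7.1:

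> If a Month 7 anti-HBs value exists, it alone determines the primary endpoint and the subject stays in the analysis. The early-termination rule applies only to subjects who leave without a Month 7 sample, and uses only titres taken before any non-study hepatitis B vaccine, immunoglobulin or blood product.

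This concerns how the endpoint is derived, not how subjects are managed, and it needs no new data. The cost is a short text change in both documents and a reported SPR that may be slightly less favourable.
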